The goal of our project is to collect 1,200,000 speech samples from 2,000 people with dysarthria, where we expect to collect data from 400 people each from five different patient populations. Each person would provide 600 speech samples.

(600 samples/person x 400 persons/etiology x 5 etiologies = 1,200,000 samples)

Our schedule of research procedures is:

1. February or March-August 2023: data collection of speech samples from 400 people with Parkinson's. Parkinson's Disease is "etiology 1".
2. August 2023-August 2024: data collection of speech samples from 1,600 people with other etiologies to be determined (i.e., voted on by our Advisory Committee). One of these etiologies will be ALS. The other three etiologies are to be determined.

In Year 1, we focus on people with Parkinson's and therefore, recruitment will be managed by our partner the Davis Phinney Foundation, a well-known non-profit advocacy group for people with Parkinson's. DPF will distribute our recruitment flyer (see **Attachment 3, recruitment for speech**) and engage in informational sessions with potential participants. (In Year 2, we will do the same procedure for other populations of interest, such as ALS patients. Therefore, in Year 2, we will add additional patient advocacy organizations to assist in recruitment, such as Team Gleason to recruit patients with ALS.)

Data collection of speech samples in Year 1 will be a collaboration of UIUC and LSVT Global team members. Potential participants will be screened both with a questionnaire and by providing a short set of "quality control" speech samples (**Attachment 4**). If the participant does not pass screening, they will be thanked for their interest. Otherwise, the participant is eligible for the study and can do the informed consent process (**Attachment 5**) and then engage in contributing speech samples (**Attachment 7**).

Participants can do as many recordings as they wish at whatever time of day is convenient for them. Participants will be able to login to the system at any time, 24/7.

In Year 2, this procedure will be performed with patients from other etiologies with additional advocacy organizations as partners.

Participants also have the option to provide additional data about themselves, such as their age, race and ethnicity, year of their diagnosis, and other information as shown in **Attachment 9**. These "metadata tags" are completely optional but are helpful for analysis.

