16D. Describe provisions to protect the privacy interests of subjects. Separation of identifiable information from speech samples in the database. Participant's recorded speech samples are stored on a virtual machine that contains no other information contributed by the participant; on this virtual machine, the participant's identity is coded using a participant code that consists of a randomly generated sequence of letters and numbers. Participant contact information, and any other information contributed by the participant, are stored in a separate database, on a separate virtual machine, accessible only by University of Illinois employees with administrative access to the server. Both virtual machines are implemented on the Beckman Institute Dell EMC Isilon/PowerScale encrypted storage array. The Isilon system currently has storage to accommodate approximately 1 PB of data, with over 300 TB of open space available. We can add additional storage, up to a maximum of 64 PB, by adding additional nodes to the array. The primary system is in a secure server room in the Beckman Institute building, and the disaster recovery (DR) system is in a secure data center on the Illinois State University campus. Both systems are fully encrypted and connected on the University of Illinois WAN. The data is synchronized from the production site to the DR site 3 times a day. Snapshots of the data are taken 3 times a day, and each is retained for 4 weeks. In addition, a monthly snapshot is taken and retained for 12 months. Participant speech data, and text transcripts created by University of Illinois annotators, will be distributed to coalition partners approximately once per month during the period of data collection and annotation. Each data distribution will consist of a single archive file, compressed and encrypted using a secure key technology such as RSA or DSA, so that it can only be decompressed by individual researchers who have been authorized by the coalition partner company under the terms of the data use agreement. Data distributions to coalition partners will never contain any information contributed by a participant other than their recorded speech samples.

16E. Describe the training and experience of all persons who will collect or have access to the data. The team members are up to date on CITI modules and Research IT trainings on data privacy and security.

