4.1 Organization represents and certifies that (i) it will provide Data composed solely of anonymized, pseudonymized, or otherwise de-identified data; (ii) it will provide Data to the Data User that does not violate any laws, rules, standards, or regulations governing the use of personal data, including but not limited to United States privacy laws and biometric laws; (iii) it will obtain all consents, waivers and clearances required to provide the Data to the Data User and for the Data User to process the Data for the Permitted Purpose, subject to the terms of this Exhibit C and the Agreement; and (iv) it will promptly delete any Data from the centralized repository following a data contributor's withdrawal of consent and/or request for data deletion and promptly notify Data User of the same.

4.2 EXCEPT AS PROVIDED IN SECTION 4.1 ABOVE, THE DATA IS PROVIDED ON AN "AS IS" BASIS, WITHOUT WARRANTIES, CERTIFICATIONS, OR CONDITIONS OF ANY KIND, EITHER EXPRESS OR IMPLIED INCLUDING, WITHOUT LIMITATION, ANY WARRANTIES, CERTIFICATIONS, OR CONDITIONS OF TITLE, NON-INFRINGEMENT, MERCHANTABILITY OR FITNESS FOR A PARTICULAR PURPOSE.

5. Termination, Terms and Conditions, Notices

5.1 Organization may terminate Data User's license to the Data upon written notice if Data User does not follow the terms of this Exhibit C, including the limitations set forth in Section 2, and does not fully cure such failure within thirty (30) days of receiving written notice from Organization. In the event Data User's license is terminated under this Section 5.1, Data User shall cease use of the Data and any Modifications and use reasonable efforts to delete any copies of the Data, but shall not be restricted from continued use of any Results.

5.2 Data User may terminate its license to the Data upon written notice to Organization. In the event Data User's license is terminated under this Section 5.2, Data User shall not receive access to additional Data following termination, but shall not be restricted from continued use of the Data to which Data User was previously granted access pursuant to this Exhibit C or to any Modifications.

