Thank you! Now, you can start recording your samples at any time. You may do these recordings at any time at your own convenience. We estimate that providing the full set of samples will take about 10 minutes total of your time. After you have submitted the full set of speech samples, the UIUC research team will evaluate the quality of your recordings. Within one week, the UIUC research team will contact you to either confirm that you may continue to participate in the study, to work with you to improve your recording environment, or to let you know that you will not be asked to participate any further in

this study. If you are not eligible to be in the study based on your speech samples, we will delete all of your data including your email address. If you have questions, please contact *<Insert name, telephone number, email address of research team member>*.

NOVA H Attachment 7

Examples of research materials for speech sample data collection

- You will be speaking many different sentences and phrases.
- Our goal is to get many different types of speech from many different people.
- Sometimes, you will be reading aloud digital assistant commands. These are common phrases that people may ask their phone or smart speaker to help them with.
- Example: What is the weather today?

- Sometimes, you will read aloud sentences that have been randomly selected from novels.
- Example: You would never have believed that one small elbow could make such a big hole
- Some of the sentences may seem silly, or not make much sense. Please just read it as automatically as you can.

- Lastly, sometimes you will speak a little longer by answering some conversational questions.
- Example: What is a favorite tv show of yours and why?

❑ In summary, there are 3 sections.

1. 30 digital assistant commands
2. 10 sentences from novels
3. 5 open questions

Block One

Section 1:

Digital Assistant Commands

What song is this?

Pause the music.

Resume.

Play music.

Stop.

Play some Beatles
music.

Play my dance
playlist.

Set the volume to 5.

Turn up the sound.

Skip backward
2 minutes.

Play hip hop music.

Skip forward 30
seconds.

Decrease volume.

Skip this track.

Brighten the office lamp.

Turn on all switches.

Dim the living room
lights.

Raise the
temperature.

Set the heat to 68.

Turn off cooling.

Answer the door.

Lock the front door.

Broadcast
‘I’m home.’

What's the
weather like
today?

Do I need an
umbrella today?

What's today's news?

Who won the NFL

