game yesterday?

What movies came
out last week?

Answer the call.

Hang up.

Block One

End of Section 1.

Thank You!

Block One

*Section 2:
Sentences Selected from
Novels*

Block One

Reminder: Some of these sentences might not make sense. Read them as naturally as you can! It's OK to make mistakes!

I'm sure I don't know
how it happened.

You would never have
believed that one
small elbow could
make such a big hole.

But it is too late.

It's not more than half
an hour since Uncle
George and Aunt Bella
went.

I'll have you ready in a
twinkling.

But the fire and the
children!

Father says that this
was very wrong of
him, and I suppose it
was, since he says so.

But I don't see how
Father could do
anything wrong.

Anyway, he had a
sister Esther whom he
loved very much.

We had to hurry to fix
the kite if we wanted
to send it up before
the wind fell.

Block One

End of Section 2.

Thank You!

Block One

Section 3: Open Questions

Block One

*Answer each question using
one or more sentences.*

*Don't read the question out
loud – just speak your
answer!*

Tell us about one
of your favorite
bands or singers.

Tell us about one
of your favorite TV
shows.

What kind of music
do you dislike, and
why?

Tell us how to
make your favorite
sandwich.

Tell me all the steps involved in withdrawing money from a bank account, as if I had never done it before.

Block One

End of Section 3, and

End of Block One!

Thank You!

NOVA H Attachment 9 optional metadata

You have the option of providing extra information to help researchers interpret your speech recordings. Providing answers to such questions is not a requirement for participation in this study; if you prefer not to answer, you will be able to choose the option "Prefer not to answer."

This information will only be used to confirm diverse representation in this data collection, and, if provided, will not be shared outside of the UIUC research team.

1. Do you consider yourself to be a member of one of the following racial groups?

- a. Answers: choose from
 - i. American Indian or Alaska Native,
 - ii. Asian,
 - iii. Black or African American,
 - iv. White,
 - v. Some other race (text box to allow description),
 - vi. Prefer not to answer

2. Do you consider yourself to be Hispanic or Latino/a?

- a. Answers: choose from Yes, No, Prefer not to answer

3. What is your gender?

- a. Answers: Male, Female, Non-binary, Prefer not to answer

4. How old are you?

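### Open answers may contain spoken identifiers; the readable plan describes no check for them before the monthly release, and the risk section omits this route

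*Combined protocol and SAP*

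**What the plan says.** Attachment 7 describes a block as three sections: "30 digital assistant commands", "10 sentences from novels" and "5 open questions". The first two are read from a script. In the third the participant speaks freely, in one sentence or more, and is told only not to read the question aloud. The five questions shown concern a favourite band or singer, a favourite television show, disliked music, a sandwich recipe, and a bank withdrawal: "Tell me all the steps involved in withdrawing money from a bank account, as if I had never done it before".

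On release, 16D states: "Participant speech data, and text transcripts created by University of Illinois annotators, will be distributed to coalition partners approximately once per month". It describes a random participant code, separate virtual machines for speech and for contact information, and an encrypted archive for each release. 13B adds that recordings count as identifiable, that no other identifying information is kept in the same database as the audio, and that recipients must sign a data use agreement.

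In Exhibit C 4.1(i) the university certifies that "it will provide Data composed solely of anonymized, pseudonymized, or otherwise de-identified data". 13A names one way privacy could be lost: a recipient institution violates its agreement and releases samples to people whom the agreement does not cover.

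**The concern.** The code and the separate machines control what is filed with a recording. They do not control what the participant says in it. A participant who mentions a full name, a street or an account detail while answering places it in the audio and, once transcribed, in searchable text. If nothing intercepts it, routine delivery sends it to every partner with nobody in breach.

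Later correction is limited. Under Exhibit C 4.1(iv), withdrawal of consent or a deletion request leads to deletion from the central repository and notice to the partner. Under 5.2, a partner that ends its own licence may go on using data it already holds. A check is therefore worth most before release. Participants are also entitled to a risk description that includes this route.

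**Working it through.** **1. The plan's own total.** 7F states the aim: "The goal of our project is to collect 1,200,000 speech samples from 2,000 people with dysarthria". Its arithmetic is "600 samples/person x 400 persons/etiology x 5 etiologies = 1,200,000 samples". The product 600 × 400 × 5 = 1,200,000 reproduces. The project has no hypothesis test, so no power calculation applies.

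**2. Share of open answers.** Inputs from Attachment 7: 30 commands, 10 novel sentences, 5 open questions.

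- Items per block: 30 + 10 + 5 = 45
- Open share: 5 / 45 = 11.1%
- Blocks in 600 samples: 600 / 45 = 13.3, not a whole number
- Per person: 600 × 5/45 = 66.7 (65 with 13 full blocks, 70 with 14)
- Per 400-person cohort: 400 × 66.7 = about 26,700
- All 2,000 people: 1,200,000 × 5/45 = about 133,000 (65 × 2,000 = 130,000 with 13 full blocks)

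This assumes that every block has the example's mix. Attachment 7 is headed as examples, so the true mix could differ.

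**3. Answers that might carry an identifier.** The documents give no rate *q* per open answer. The rates below are assumptions, set wide on purpose. Expected count = 133,333 × *q*. The chance that a given participant has at least one is 1 − (1 − *q*)^66.7, treating answers as independent.

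| Assumed *q* | Samples affected | Chance per participant |
|---|---|---|
| 0.01% | 13 | 0.7% |
| 0.1% | 133 | 6.5% |
| 1% | 1,333 | 49% |
| 5% | 6,667 | 97% |

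The range runs from a handful to several thousand. The table shows only that the number depends on a quantity nobody has stated.

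**4. Safeguards set against a spoken identifier.**

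| Safeguard | Does it reach a name spoken in an answer? |
|---|---|
| Random code, separate machine (16D) | No; these act on labels and stored contact details |
| No other identifying information with the audio (13B) | Not assured; the name is inside the audio |
| Only speech samples and transcripts released (16D) | No; the name is part of both |
| Encrypted archive (16D) | Protects transit, not what an authorised recipient hears or reads |
| Limits on redistribution, disclosure and identification (Exhibit C 2.1, 3.1, 3.3) | Limits onward use; does not stop delivery to the partner |
| Annotation of all samples (7F) | Could, but is not described as an identifier check |
| Quality control checks (12D) | Described alongside sentence counts and payment, not content |

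**The case against.** The case on the other side is substantial, and several parts of it stand.

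- *The prompts do not seek personal details.* This stands. The bank question asks for generic steps, not the speaker's bank or account. A reader might infer that the prompts solicit personal narrative; the documents support only incidental disclosure. 7D plans samples of about 5 to 10 seconds, and Attachment 7 says open answers run slightly longer, so unbounded storytelling is not supported either.
- *The certification accepts pseudonymized data.* This stands. The clause offers three alternatives and the recordings are coded. A reader might infer that the certification is false for open answers. The documents do not establish that. They leave it unassured for any answer in which an identifier happens to be spoken, because a code on the file does not mask a name in its content.
- *The agreement and encryption do cover content.* This stands, with the limit shown above: they govern what happens around and after delivery.
- *A check may exist.* This stands. 16B lists removal of direct identifiers as an option, but the tick marks cannot be read. The consent form and other pages are not available, and Attachment 7 is not the full instruction set. A reader might infer that no screen exists; the documents show only that none is described in the readable text.
- *All audio is already treated as identifiable.* 13B says so, while 7F calls the shared data deidentified. That wider tension covers every sample and deserves reconciling. It does not dispose of this point: a transcript carries no voice, so a name in it is a separate and directly searchable identifier.

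**Conclusion.** The point holds as a gap in what the plan describes, not as a demonstrated release of identifying data. Three facts carry it: open answers are unscripted, with no instruction shown to leave identifiers out; audio and transcripts are delivered about monthly; and no readable step screens spoken content. In addition, the privacy risk in 13A omits a route that requires no breach.

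About 11% of samples are exposed to this possibility, roughly 130,000, if other blocks resemble the example. How many would contain an identifier cannot be estimated from the documents. The recommendation does not depend on that number, because the remedy is cheap and release is hard to undo. If the unreadable or removed pages already describe a screen, what remains is to state it in 16D and complete 13A and 13B.

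**What to change.** 1. **Attachment 7, Section 3 instruction slide:** add one line asking participants not to state full names, addresses, account details or similar identifying facts.
2. **16D:** state that annotators flag any open answer containing a spoken identifier, and that its audio and transcript are withheld or redacted before each monthly archive is built. If such a check is already in place, describe it there.
3. **13A and 13B:** add spoken identifiers as a route to loss of privacy, with items 1 and 2 as the mitigation.

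The cost is one slide line, one annotation flag and one release filter. University annotators already produce the transcripts, so the flag adds slightly to existing work. Some open answers would be lost or edited: even at the highest rate assumed above, 6,667 / 1,200,000 = 0.56% of all samples, and 5% of open answers.

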10D. Describe procedures to assure equitable selection of subjects. Justify the use of the groups marked in Section 9B. Selection criteria that target one sex, race, or ethnic group require a clear scientific rationale.

We will offer participants the optional ability to provide demographic data, so that we can assess the diversity and equitable representation of our sample.

Section 11. RECRUITMENT

11A. Select all recruitment procedures that will be used.

- Student subject pool, *please specify*:
- Email distribution
- MTurk, Qualtrics Panel, or similar online population, *please specify*:
- US Mail
- Flyers/brochures
- Website ad, online announcement (e.g. eWeek), or other online recruitment, *please specify*: newsletter announcements via organizations that advocate for and support people with disabilities.
- Newspaper ad
- Verbal announcement
- Other, *please specify*:
- Not applicable (secondary data only)

11B. Drafts or final copies of all recruitment materials (including verbal scripts) are attached.

Yes Not Applicable

11C. For each group of participants, describe the details of the recruitment process.

In Year 1, Davis Phinney Foundation will include our recruitment flyer in their distribution channels, will also host optional information and Q&A sessions with potential participants, and will answer individual questions as needed from potential participants. The UIUC Speech Accessibility Project's website will remain as a public source of information, including an updated FAQ list that may be updated based on feedback from DPF.

Section 12. REMUNERATION AND PLAN FOR DISTRIBUTION

Refer to the University [Business and Financial Policies and Procedures](#) for further guidance on the compensation process and reporting requirements.

12A. Will subjects receive inducements or rewards before, during, or after participation?

Yes No

If yes, complete the rest of Section 12. If no, proceed to Section 13.

12B. Select all forms of remuneration that apply.

- Cash, *please specify amount*:

Check, please specify amount:
 Gift Certificate, please specify amount: Amazon ecodes adding up to \$180 per data contributor and up to \$90 per caregiver.
 Lottery, please specify amount: and odds:
 Course Credit, please specify amount: and specify equivalent alternative activity:
 Other, please specify:

12C. Will payment be prorated before, during, or after participation?

Yes, please specify how: prorated by number of recorded sentences uploaded to our system

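### The race item is worded for one answer, so if built as worded it leaves people in two or more listed groups out of at least one representation count

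*Combined protocol and SAP*

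**What the plan says.** Attachment 9, item 1 asks "Do you consider yourself to be a member of one of the following racial groups". The response instruction is "Answers: choose from", followed by six options: four named racial groups, an option worded "Some other race (text box to allow description", and a choice not to answer. Item 2, on Hispanic or Latino/a ethnicity, uses the same instruction: "choose from Yes, No, Prefer not to answer".

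The introduction to Attachment 9 tells participants what the answers are for: "This information will only be used to confirm diverse representation in this data collection". Section 10D, which asks how equitable selection will be assured, answers only that optional demographic data will be collected "so that we can assess the diversity and equitable representation of our sample". Section 7F adds that the optional tags are useful for analysis but specifies no analysis. Sections 7F and 10A set the planned size at 2,000 participants, and Section 7F splits it into 400 in each of five etiologies.

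**The concern.** The stem speaks of membership of one group, and nothing in the item invites a second answer. A person who belongs to two of the named groups can pick one of them, use the free-text category or decline. No listed option records both memberships.

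The accuracy of the race part of the representation check is at stake. A count that omits people because of how the question was put can make a group look less well represented than it is. Nothing in the resulting table would show that this had happened.

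**Working it through.** The documents state no figure on this point, so there is nothing to reproduce. The check is a reading of the text followed by a simple count.

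**Step 1: does the wording point to one answer?**

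- The stem of item 1 refers to one of the groups, in the singular.
- The instruction gives no number of selections, and no select-all wording appears.
- Item 2 uses the same instruction for answers that exclude each other. This supports a single-choice reading of item 1 but does not prove it.
- Item 1 puts the option to decline in the same list as the groups, as the single-choice items 2 and 3 do.
- Item 6 of the same attachment explicitly allows for more than one language. Item 1 has no comparable signal.

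A developer working from this text would most naturally build a single-select field.

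**Step 2: what follows under single choice?**

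Take a person who belongs to k of the named groups, with k at least 2.

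- If they pick one named group, they are missing from k − 1 group counts.
- If they use the free-text category, they are missing from all k, because no rule codes the text back to named groups.
- If they decline, they are also missing from all k.

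In each case they are missing from at least one count.

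**Step 3: how many people?**

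Inputs:

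- N = 2,000 overall and 400 per etiology (Sections 7F and 10A).
- p = share of participants belonging to two or more named groups. The documents do not give it; 1% to 10% is an assumption for illustration.
- Everyone answers the item. This is also an assumption, since the item is optional; the number of respondents affected falls in proportion to the response rate.

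People missing from at least one count = N × p.

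| Assumed p | Of 2,000 | Of 400 |
|---|---|---|
| 1% | 2,000 × 0.01 = 20 | 400 × 0.01 = 4 |
| 3% | 2,000 × 0.03 = 60 | 400 × 0.03 = 12 |
| 10% | 2,000 × 0.10 = 200 | 400 × 0.10 = 40 |

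If the field is built as multi-select, every entry is 0.

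**Step 4: how large is the error for one group?**

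Let a be the members counted in a group and m the members who gave another answer because only one was possible. The group is understated by m / (a + m). The documents supply neither a nor m, so no group-specific figure can be given.

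**The case against.** The strongest reply is that the single-answer format is inferred. Elsewhere the documents name the control: drop-down and menu fields in the Attachment 4 questionnaire, scroll menus in Attachment 9 items 4 and 5. Item 1 names none. Its stem could be read as asking about membership of any listed group, and item 2 is single-choice because its answers exclude each other, whatever the instruction says. This stands as a limit on certainty. It does not remove the point, because wording meant to allow several answers still steers respondents to one.

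The reply is also right that little depends on the counts. There is no race quota, numerical representation target or hypothesis test, and Attachment 9 says the answers stay within the university's research team.

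A reader might infer four stronger things, none of which the documents support:

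- *The form accepts only one answer.* The response format is never stated.
- *Race counts are the only check in Section 10D.* That section relies on demographic data in general, and Attachment 9 also collects ethnicity, gender, age range, state and language background. Optional demographic data as a whole is the only stated check.
- *The loss is permanent.* Contact information is stored (Section 16D) and the identity key is kept at least three years after the last recording (Section 16C), so participants could be asked again. Some may also have described themselves in the text box.
- *The smallest groups are hit hardest.* The ratio in Step 4 depends on how many members have more than one identity and which option they choose, not on group size as such.

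**Conclusion.** The concern holds as a minor point about a data-collection item. The bias arises if the field is built the way the item reads, and it has one direction: a named group can lose members who also belong to another group, and the format adds none wrongly. The range of 20 to 200 of 2,000 rests on an assumed share and on full response, neither of which the documents supply. It should be read as an indication of scale, not an estimate. The effect stops at the descriptive race counts; eligibility, enrollment targets and the speech data are untouched.

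**What to change.** Reword item 1 along these lines: *Which of the following racial groups do you consider yourself a member of? Select all that apply.* Make the field multi-select and keep the option to decline, set so that it cannot be combined with a group.

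State in the plan that free text naming a listed group will be coded back to that group. Report each group in two ways: those who chose it alone, and those who chose it alone or in combination.

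The cost is one phrase, one field setting and a short coding rule, with essentially no added burden on participants. The one drawback is that group percentages can add to more than 100%, which a table footnote can explain. The change is best made before collection starts. If answers have already been collected with a single-select field, the affected participants would have to be asked again, which takes far more effort.
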